7.7 Calculations Using Dates

The following conventions will be used to calculate analysis day for reporting purposes:

- Analysis Day = date of measurement analysis day 1 +1, if date of measurement is on or after analysis day 1.
- Analysis Day = date of measurement analysis day 1, if date of measurement is prior to analysis day 1.

Study day will be presented in applicable listings where the calculated analysis day of the measurement is negative due to the definition of baseline for rollover subjects with treatment gaps prior to enrollment in the open-label extension. The following conventions will be used to calculate study day for reporting purposes:

- Study Day = date of measurement study day 1 +1, if date of measurement is on or after study day 1.
- Study Day = date of measurement study day 1, if date of measurement is prior to study day 1.

8 Summary Population

8.1 Disposition of Subjects

Disposition data from each study will be integrated, listed, and summarized for the Safety population.

A frequency table by treatment/analysis group and overall will include the number and percentage of subjects along with last available completion status.

A separate table will show the number (%) of subjects who withdrew and the primary reason for withdrawal, by treatment/analysis group and overall. The primary reasons of withdrawal reported by subjects will be presented in this table. The number (%) of subjects who discontinued study drug and the reason for early discontinuation will be summarized in a

separate table. Subjects may contribute more than one event to the summary table since it is possible for a subject to discontinue from more than one study. A footnote indicating the number of subjects with multiple study discontinuations will be included in the summary table.

The time to discontinuation of study drug will be analyzed. The time to discontinuation is defined as the number of days from the Analysis Day 1 date to the last dose of study drug for a particular treatment. Subjects will be censored if no early study drug discontinuation occurred. The median duration and the associated 95% confidence interval for each treatment group will be estimated using the Kaplan-Meier method (log-log transformation). Kaplan-Meier estimates of the survival function will be calculated and displayed graphically.

8.2 Protocol Deviations

Protocol deviations data will not be integrated. Summaries are available in the individual study results.

8.3 Demographic and Baseline Characteristics

Demographic and baseline characteristic data will be integrated, listed, and summarized for the Safety population.

The following demographic information will be summarized by treatment/analysis group and overall.

- Age (years), calculated as (informed consent date birthdate +1)/365.25
- Age Categories (<65, >=65)
- Sex (male/female)
- Race (White, Black, American Indian/Alaska Native, Native Hawaiian or Other Pacific Islander, Asian, Other)
- Ethnicity (Hispanic or Latino, Non-Hispanic/Non-Latino)
- Height (cm)
- Body Weight (kg)
- Body mass index (BMI)
- eGFR provided by the central lab using subject data and MDRD-NKDEP equation

8.4 Medical History

General medical history data will not be integrated. Summaries are provided in the individual study results.

Parkinson's disease history data including the following will be integrated, listed, and summarized for the Safety population by treatment/analysis group and overall.

- Age (years) at PD diagnosis
- Time since PD diagnosis in years
- Age (years) at start of levodopa treatment
- Duration of levodopa treatment in years
- Duration of levodopa-induced dyskinesia in years
- Baseline Levodopa dose

For the duration of Parkinson's disease, if only the month and year of diagnosis is available, the 15th day of the indicated month is assumed, and when only the year of diagnosis is available, July 1 of the indicated year is assumed. A similar algorithm is used for age at PD diagnosis, age at start of levodopa treatment, duration of levodopa treatment, and duration of levodopa—induced dyskinesia. Fractional years of duration will be used for the analyses.

8.5 **Prior and Concomitant Medications**

Prior medications are defined as medications with a stop date occurring before the first dose date. Concomitant medications are defined as medications with a stop date occurring on or after the first dose date, or listed as ongoing. Medications with start and stop dates (or ongoing) which bracket the first dose date will be summarized as both prior and concomitant medications.

All non-study drugs (including prescribed and over the counter medications) taken are collected on the CRFs for the individual studies.

Prior and concomitant medication data will be integrated, listed, and summarized by Anatomical Therapeutic Chemical (ATC) Level and preferred term (PT) by treatment/analysis group for the Safety population. At each level of summarization, a subject is counted once if he/she reported one or more medications at that level. The PD prior and concomitant medications will be presented separately.

For the purpose of classifying medications as prior and/or concomitant in summaries, incomplete medication start and stop dates will be imputed as detailed below:

- If year and month are present and day is missing then set start day to last day of month, and set end day to the later of (first day of month, start day)
- If year and day are present and month is missing then set start month to December, and set end month to the later of (January, start month)
- If year is present and month and day are missing then set start month and day to December 31st, and set end month and day to the later of (January 1st, start month and day)
- Completely missing dates will not be imputed

If start date is completely missing and end date is after the first dose, then the medication will be classified as both prior and concomitant. If the end date is missing, then the medication will be classified as ongoing. Medications for which the start and end dates are missing will be classified as prior and concomitant.

8.6 Parkinson's Disease-Related Baseline Characteristics

Parkinson disease related baseline characteristic data will be integrated, listed, and summarized for the Safety population.

- MDS-UPDRS: Part I, Part II, Part III, Combined (Parts I, II, and III), Part IV, Part IV item 4.1, Part IV, item 4.2
- MMSE score
- Hoehn and Yahr Stage

8.7 Physical Examination

Physical examination data will not be integrated. Summaries are available in the individual study results.

8.8 Treatment Compliance

Treatment compliance data will not be integrated. Summaries are provided in the individual study results.

9 Safety Analysis

Safety endpoints will be summarized using integrated data by treatment/analysis group from the time of first dose and include all available safety data. No formal statistical testing is planned.

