2.1 Safety Summary

Safety and demographic data from:

- ADS-PAR-AM201
- ADS-AMT-PD301
- ADS-AMT-PD302

will be integrated for purposes of further characterizing the safety of ADS-5102. See Section 5.1 for a detailed description of the Safety population.

3 Studies to be included

The following studies will form the basis of the submission:

• ADS-PAR-AM201, a phase II/III, multi-center, randomized, double-blind, placebo-controlled, 4-arm parallel group study of ADS-5102 in subjects with PD who have LID. 83 subjects were randomized in a 1:1:1:1 ratio to one of four treatments (Placebo, 260 mg ADS-5102, 340 mg ADS-5102, or 420 mg ADS-5102). Subjects who were assigned to Placebo or 260 mg ADS-5102 received the same nightly dose throughout the entire 8-week dosing period. Subjects who were assigned 340 mg ADS-5102 or 420 mg ADS-5102 received, in double-blind fashion, escalating doses of ADS-5102 as indicated in Table 1:

Table 1: ADS-PAR-AM201 Dose Escalation

		Dosing Days 1–7	Dosing Days 8–14	Dosing Days 15–56
Treatment		(Week 1)	(Week 2)	(Weeks 3–8)
Placebo Placebo		Placebo	Placebo	Placebo
260	mg ADS-5102	260 mg ADS-5102	260 mg ADS-5102	260 mg ADS-5102
340	mg ADS-5102	260 mg ADS-5102	340 mg ADS-5102	340 mg ADS-5102
420	mg ADS-5102	260 mg ADS-5102	340 mg ADS-5102	420 mg ADS-5102

The primary objective of the study was to evaluate the efficacy of each of three dose levels of ADS-5102 oral capsules dosed once nightly for the treatment of LID in subjects with PD. The secondary objectives of the study was to evaluate the potential efficacy of each of three dose levels of ADS-5102 for the treatment of PD-related fatigue, to evaluate the safety and tolerability of each of three dose levels of ADS-5102 in this study population, to select an appropriate dose level of ADS-5102 dosed once nightly for future trials, and to measure steady-state amantadine concentrations at each of three dose levels of ADS-5102 dosed once nightly.

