- ADS-AMT-PD301, a phase III, multi-center, randomized, double-blind, placebo-controlled, 2-arm, parallel group study of ADS-5102 in subjects with PD who have LID. 126 subjects were randomized in a 1:1 ratio to placebo or active (340 mg ADS-5102). Study medications were administered as 2 capsules once nightly at bedtime (if possible, no earlier than 9 pm) for 25 weeks. The primary objective of the study was to evaluate the efficacy of ADS-5102 oral capsules, an extended release formulation of amantadine, at a dose level of 340 mg, dosed once nightly at bedtime, for the treatment of levodopa induced dyskinesia (LID) in subjects with Parkinson's disease (PD). The secondary objective was to evaluate the safety and tolerability of ADS-5102 in this study population.
- ADS-AMT-PD302, a phase III, multi-center, open-label study of ADS-5102. Up to 250 subjects will be enrolled with each belonging to one of the following three groups:
 - 1. Group 1 (current Adamas LID study subjects): Subjects who are participating in Adamas efficacy studies evaluating ADS-5102 in LID and choose to immediately transition into ADS-AMT-PD302 without a time gap
 - 2. Group 2 (previous Adamas LID study subjects): Subjects who have previously participated in Adamas efficacy studies evaluating ADS-5102 in LID and will enter ADS-AMT-PD302 after a time gap
 - 3. Group 3 (non Adamas LID study subjects with prior DBS): Subjects who would have been deemed ineligible for participation in previous or current Adamas efficacy studies due to having undergone deep brain stimulation

The primary objective of the study is to evaluate the safety and tolerability of ADS-5102 oral capsules, an extended release formulation of amantadine, administered at a dose of 340 mg once nightly at bedtime for the treatment of levodopa induced dyskinesia (LID) in subjects with Parkinson's disease (PD). The secondary objectives of the study are to evaluate duration of ADS-5102 effect on dyskinesia as assessed by the Unified Parkinson's Disease Rating Scale (MDS-UPDRS), Part IV and to evaluate clinical progression of Parkinson's disease as assessed by MDS-UPDRS, Combined Score, Parts I, II, and III.

4 Planned Analyses

Analyses will be performed after database locks for ADS-PAR-AM201 and ADS-AMT-PD301, and database freeze for ADS-AMT-PD302.

5 Analysis Sets

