7.2 Treatment Assignments and Analysis Groups

Treatment will be assigned using the treatment assignments from the individual studies.

Integrated listings will display the treatment received at the time the data was collected.

The following treatment/analysis groups will be included in summary tables, in the order shown:

- Placebo
- 340 mg ADS-5102
- \geq 340 mg ADS-5102
- ADS-5102

Individual summaries for 260 mg ADS-5102 and 420 mg ADS-5102 will not be included, but are available in the study results for ADS-PAR-AM201.

Since subjects may have received more than one treatment or ADS-5102 dose-level, they may be counted multiple times in summary tables, but will appear at most once in each treatment/analysis group and at most once in the overall column (where displayed).

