9.2 Adverse Events

An adverse event (AE) is any untoward medical occurrence that occurs in conjunction with the use of a medicinal product in humans, whether or not considered to have a causal relationship to the medicinal product. An AE can, therefore, be any unfavorable or unintended sign (including a clinically significant abnormal laboratory finding), symptom, or disease

temporally associated with the use of a medicinal product, whether or not considered related to the medicinal product.

Adverse event data will be integrated, listed, and summarized for the Safety population. Events will be presented according to MedDRA® system organ class (SOC) and preferred term (PT). Summaries will be ordered alphabetically by SOC and PT, and by decreasing frequency of preferred term among all treatment/analysis groups regardless of whether a "total" column is presented.

Partial (Incomplete) AE onset and end dates will be listed as such. All AEs collected on the AE eCRF page will be considered treatment–emergent.

Most commonly reported (at least 2% of either active or placebo treatments) AEs will be presented by preferred term, and summarized by treatment/analysis group.

For each summary, at each of the SOC and PT levels, a subject will be counted once if he/she reported one or more AEs. Percentages will be calculated out of the number of subjects in the Safety population.

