9.2.8 Adverse Events of Special Interest

Adverse events of special interest are grouped into three event categories: Neuropsychiatric (CNS), Falls, and Hallucinations. The CNS category combines the following SOCs: Nervous system disorder and Psychiatric disorder. The Falls category combines all PTs that contain the term "Fall" or "Falls". The Hallucinations category combines all PTs that contain the term "Hallucination".

Event incidence will be summarized treatment/analysis group.

Time to onset will be analyzed and is defined as the number of days from the first dose of study drug to the onset of the first AE in the category. Subjects will be censored at the latest date known not to have had such AE. The median time to event and the associated 95% confidence interval for the Placebo and 340 mg ADS-5102 treatment groups will be estimated using the Kaplan-Meier method. Kaplan-Meier estimates of the survival function will be calculated and displayed graphically.

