9.3 Clinical Laboratory Evaluations

Clinical laboratory data for liver and renal function parameters will be integrated, listed, and summarized for the Safety population. Summaries for all other parameters are available in the individual study reports.

Laboratory assessments for these parameters were performed by a central laboratory. All summaries will be based on the SI units provided by the central lab.

Maximum on-treatment values will be summarized for the liver function parameters and minimum on-treatment values will be summarized for the renal function parameters. For both groups, the change from baseline to the maximum/minimum value will be presented.

All clinical laboratory measures will be classified as Low, Normal, or High, or Normal/Abnormal according to the normal ranges. These categorical data will be summarized in shift tables comparing the results at the baseline visit with the most abnormal results over the treatment period.

Liver function parameters include:

- Bilirubin
- Alkaline phosphatase
- γ-glutamyltransferase
- Alanine aminotransferase
- Aspartate aminotransferase

Renal function parameters include:

- Blood urea nitrogen
- Creatinine
- Estimated GFR MDRD-NKDEP
- Estimated GFR Cockcroft-Gault

Estimated GRF – Cockcroft-Gault values are not reported in the individual study databases and will be calculated as follows:

Integrated Summary of Safety for ADS-5102

Date Issued: 13Nov2015

eCreatinine Clearance $(ml/min/1.73 m^2) =$

[1.73 \times (140 – age) \times wt (kg) \times (0.85 if female) / Serum creatinine (mg/dL) \times 72 \times Body Surface Area;

Creatinine in mg/dL is rounded to 1 decimal place prior to applying the Cockcroft-Gault equation.

The equation to calculate Body surface area is described as following:

Body Surface Area(m²) = [weight (kg) \times height (cm)/3600]^{1/2}

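### The integrated safety tables set 8 to 25 weeks of placebo beside drug columns that include open-label PD302, with no controlled-period, by-study or person-time version for adverse events, laboratory tests or vital signs

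*SAP*

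**What the plan says.** SAP Section 9 sets the rule for all safety outputs: "Safety endpoints will be summarized using integrated data by treatment/analysis group from the time of first dose and include all available safety data". It adds: "No formal statistical testing is planned". Under Section 2.1 the data "will be integrated for purposes of further characterizing the safety of ADS-5102".

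- **Studies and timing.** Section 3 describes AM201 (83 subjects, 1:1:1:1, 8 weeks), PD301 (126 subjects, 1:1, 25 weeks) and PD302 (up to 250, open-label). Protocol Section 6.3 confirms that every PD302 subject gets ADS-5102, and Section 6.6 allows up to 101 weeks. SAP Section 4: "Analyses will be performed after database locks for ADS-PAR-AM201 and ADS-AMT-PD301, and database freeze for ADS-AMT-PD302". No freeze date is given.
- **Columns.** Placebo, 340 mg, 340 mg or more, and any ADS-5102 (Section 7.2). For subjects with more than one treatment, "they may be counted multiple times in summary tables, but will appear at most once in each treatment/analysis group". A PD301 placebo subject who enters PD302 is therefore in the placebo column and in drug columns.
- **AEs.** Section 9.2: "Percentages will be calculated out of the number of subjects in the Safety population".
- **Laboratory tests and vital signs.** Section 9.3: "Maximum on-treatment values will be summarized for the liver function parameters and minimum on-treatment values will be summarized for the renal function parameters". Section 9.4 uses on-study minima and maxima.
- **Time-to-event.** Kaplan-Meier is planned for study drug discontinuation (8.1) and for three special-interest categories, where the median and its "confidence interval for the Placebo and 340 mg ADS-5102 treatment groups will be estimated using the Kaplan-Meier method" (9.2.8).

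**The concern.** This SAP is for an integrated summary of safety supporting a submission. Its main AE, laboratory and vital-sign shells print Placebo first and the ADS-5102 columns beside it. Readers will compare those columns whether or not a test is run.

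The columns differ in three ways unrelated to the drug's effect:

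- **Follow-up.** Placebo stops at 8 or 25 weeks, while PD302 follow-up depends on the freeze. Crude percentages, maxima and minima all depend on time observed and number of visits.
- **Randomisation.** Most of the 340 mg column is open-label.
- **Population.** PD302 Groups 1 and 2 exclude subjects who stopped earlier for ADS-5102-related AEs, which lowers drug-column rates. Group 3 (prior deep brain stimulation) would have been ineligible for the efficacy studies, so it has no placebo counterpart.

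These can pull in opposite directions, so a reader cannot correct the columns by eye.

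**Working it through.** **1. Are the outputs missing?** Tables 1.6.1.1 to 1.6.9 (AEs), 1.7.1.1 to 1.7.2.2 (liver and renal) and 1.8 (vital signs) are summaries by pooled column or subgroup, or subject listings. None of the summaries is limited to a double-blind period, stratified by study or expressed per person-time. Disposition Tables 1.1.1 and 1.1.2 do have a row per study, so the layout exists but is not used for safety.

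**2. How much of the 340 mg column is randomised?** The plan gives no figure here. AM201 has about 21 per arm (83/4) and PD301 has 63 (126/2), so 21 + 63 = 84 were randomised to 340 mg.

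- No rollover: 84/(84 + 250) = 84/334 = 25%.
- All 63 PD301 actives roll over and count once: 84/(21 + 250) = 84/271 = 31%.

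**3. AEs with no drug effect.** Assume the same constant hazard in both columns, no dropout, and risk *p* at 25 weeks. Then risk(T) = 1 − (1 − p)^(T/25). At p = 10%, risk(8) = 3.3%.

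- Placebo, taking 22 AM201 and 63 PD301 subjects: (22 × 3.3% + 63 × 10%)/85 = 8.27%. Using 21 gives 8.33%.
- 340 mg, no rollover: [21 × risk(8) + 63p + N × risk(f)]/(84 + N).
- 340 mg, full rollover: [21 × risk(8) + 63 × risk(25 + f) + (N − 63) × risk(f)]/(21 + N).

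Here N is PD302 enrolment and f its follow-up. The third follow-up case assumes a freeze near the SAP date with uniform accrual: 14 July 2014 to 13 November 2015 is 487 days, or 69.6 weeks.

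Ratio of 340 mg to placebo (no rollover / full rollover):

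| N | f = 13 weeks | f = 26 weeks | f uniform on 0 to 69.6 |
|---|---|---|---|
| 250 | 0.74 / 0.89 | 1.19 / 1.44 | 1.46 / 1.76 |
| 150 | 0.77 / 1.04 | 1.17 / 1.55 | 1.39 / 1.85 |
| 100 | 0.81 / 1.20 | 1.14 / 1.67 | 1.34 / 1.95 |

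For N = 250 the crude 340 mg percentages are 6.1/7.4, 9.9/11.9 and 12.1/14.6, against 8.3 on placebo. In the uniform case, p = 5% gives 1.49/1.82 and p = 20% gives 1.40/1.66.

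**4. Laboratory extremes.** For independent visits, the expected maximum in within-subject SD is 0.85, 1.03, 1.16 and 1.27 for 3, 4, 5 and 6 values. Minima mirror this. With the Protocol Table 6 chemistry visits (Weeks 4, 8, 16, 28, 40, 52, 64) and uniform follow-up to 69.6 weeks, 94% of PD302 subjects have at least one value. They average 4.2 visits and an expected maximum of 0.97 SD. Neither document gives the parent-study visit counts, so I took 3 to 6.

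Pooled 340 mg minus placebo, N = 250:

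| Parent-study visits | 3 | 4 | 5 | 6 |
|---|---|---|---|---|
| No rollover | +0.09 | −0.04 | −0.14 | −0.22 |
| Full rollover | +0.20 | +0.05 | −0.06 | −0.14 |

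If everyone has 52 weeks in PD302 (6 visits, 1.27 SD), the difference runs from 0.00 (6 parent visits, no rollover) to +0.44 (3 parent visits, full rollover).

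**5. Could a reader build rates from the exposure table?** Not safely. The note to Table 1.5 keeps only PD302 exposure for subjects with a treatment gap, while AEs include all available data. Numerator and denominator would not match.

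**The case against.** The strongest reply is that the SAP promises no placebo contrast for general AEs, laboratory tests or vital signs: it is descriptive and repeatedly defers to the individual study results. A controlled pool would rest mainly on PD301, which has its own randomised results; AM201 adds about 21 per arm. This fixes the weight of the point: what is missing is a pooled controlled display, and the study reports, which I have not seen, may hold within-study comparisons. It does not make the printed columns comparable.

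There are partial safeguards. Kaplan-Meier censoring handles unequal follow-up for neuropsychiatric events (two whole organ classes), falls and hallucinations. Serious AEs are listed with study and treatment, and AE tables by prior deep brain stimulation largely separate Group 3. But the 340 mg Kaplan-Meier curve still mixes randomised and open-label subjects, and none of these replaces a controlled-period table.

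The sizes are also model-dependent. The protocol expects up to 250 enrolled to support 100 one-year completers. Read as 40% retention (100/250, exponential dropout in PD302 only), the uniform-accrual ratio at N = 250 falls from 1.46/1.76 to 1.10/1.33. If all the hazard falls in the first 4 to 8 weeks, the ratio is 0.96 to 0.98, almost no artefact. Both objections are fair, and both results lie inside the range above. They confirm that size and sign are unknown before the freeze. The laboratory result is weaker still: near the SAP date even its sign is indeterminate.

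**Conclusion.** The concern holds. With high confidence, the plan contains no AE, laboratory or vital-sign output that shows the randomised contrast across the controlled studies, and none that adjusts general AEs for time at risk.

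The size is conditional. With no drug effect, the crude AE ratio could lie anywhere from 0.74 to 1.95 over the cases tabulated, and the laboratory artefact from −0.22 to +0.20 within-subject SD near the SAP date at N = 250. These rest on equal constant hazards, independent visits, no dropout, approximate arm sizes, assumed parent-study visit counts and an assumed freeze date.

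The consequence is misreading of descriptive tables, since no test depends on them. The change should be made but does not invalidate the plan.

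**What to change.** 1. Add placebo versus ADS-5102 tables for AEs, laboratory tests and vital signs, restricted to the double-blind periods of AM201 and PD301 and stratified by study. Base any placebo comparison on these. Stratification is needed as well as restriction. Unstratified, the any-dose column averages (62 × 8 + 63 × 25)/125 = 16.6 weeks, against (21 × 8 + 63 × 25)/84 = 20.75 on placebo. That gives a crude ratio of about 0.80 under equal hazards.
2. In the all-exposure pool, add first-event rates per 100 subject-years, with events and person-time aligned for subjects with a treatment gap. State there that the placebo column is not comparable.
3. As a minor separate repair, reconcile the shell of Table 1.6.10.1, which shows event counts without N or percentages, with the subject-level counting in Section 9.2. Tables 1.6.11.1 and 1.6.12.1 repeat that shell but carry percentage notes. Those notes also contain Kaplan-Meier text and look copied, so the intended layout should be stated.

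The cost is a few outputs from data already integrated. The AM201 stratum will be imprecise (about 21 per arm against 63 in PD301). Subject-year rates dilute early-onset effects, so they supplement the controlled-period tables and do not replace them.
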